### III.b. Data Analysis and Data Monitoring

Oversight of the Data: CARE-PSP will be maintained by the Principal Investigator. The Principal Investigator will review study procedures annually and report any concerns in the IRB continuation application. This is a Level I, Low, Minimal Risk study; therefore, there is minimal risk of unanticipated problems with the exception of breaches in confidentiality. The data for the study will be entered into a secured database using an electronic data capture program such Research Electronic Data Capture (REDCap). The database will be stored on a secure password-protected server and not on individual desktop computers. The code sheet will be password protected and the password will be updated annually. Breaches of confidentiality will be reported to the IRB immediately with the “Reportable Event/Unanticipated Problem Form.”

The PI, co-investigators, and/or study staff will review all data collection forms on an ongoing basis for data completeness and accuracy as well as protocol compliance. The data will be reviewed on a quarterly basis:

- Subject accrual (including compliance with enrollment criteria)
- Status of all enrolled subjects
- Adherence data regarding study visits and procedures

Safety data (AEs and SAEs) will be reported to the Principal Investigator and reviewed per occurrence and in accordance with the IRB's regulations. Any significant findings (i.e. protocol deviations) will be reported to the IRB in accordance with requirements and will be documented accordingly.

### III.c. Data Storage and Confidentiality

All subjects will be assigned unique ID numbers. All research data files will be stored at the Rush University Parkinson's Disease and Movement Disorders Program in secured file cabinets, including case report forms for home visits, informed consent forms and informed consent documentation checklists. Data will be entered into a secured database using an electronic data capture program such Research Electronic Data Capture (REDCap). The database will be stored on a secure password-protected server and not on individual desktop computers. The code sheet will be password protected and the password will be updated annually. Hard copies of case report forms and informed consent documentation checklists will be labeled with the study ID only and maintained in individual files by study ID number. Signed informed consent forms, containing subject names, will be stored separately in the regulatory binder, which will be stored in a locked file cabinet in the PI's office.

Only the PI, Co-investigators and research staff will have access to the database and hard copies of study documents. During the consent process, the potential participant will be informed that aspects of their

PHI will be shared with collaborating researchers at Rush, including [name]; however, they will have an opportunity to decline having their PHI shared and still participate. Data will be stored in a format suitable for research inquiries by the PI and Co-Investigators, who might make use of the data in a retrospective manner for other Rush-based research studies. The data collected from this study is restricted to access by the PI and direct study collaborators at Rush, including mentors [name]. No collaborator will be allowed to share the data outside the study team without the PI's written approval. Collaborators interested in using the data outside of this study will be required to provide a written request to the PI noting the specific data fields of interest, a description of how the data will be used and who will have access/use the data. The PI reserves the right to grant/deny approval to any collaborator prior to the release of any study data. If a particular researcher/collaborator has an interest in a study population, then the PI will review the database to identify eligible subjects that meet the study inclusion criterion and the potential participant(s) will then be contacted by a member of this study team whom the subject has already met to see if they are interested in participating in the particular study. If a participant is interested, he or she will be referred to that Rush study team and will be scheduled for a separate consent procedure with the individual Rush researcher for that particular study and at that point the participant can choose whether to participate or not in that particular study. The results of the CarePSP study may be published in a book, journal, and other media or used for teaching purposes. However, all published data will be made anonymous.

#### IV. Risk/Benefit Assessment

##### IV.a. Risk

There are no known risks from participating in neurological or neuropsychological tests. Subjects may experience mild boredom or cognitive fatigue; however, most individuals with like symptoms find the tests interesting and are able to tolerate up to two-hour duration of testing well. There is, however, a risk that the study team may, in the course of any given visit to the home or contact with the subject and/or caregiver following a visit, detect evidence concerning for adult abuse or suicidal ideation. In these instances, the nurse, physician, and social worker are mandated reporters of these conditions and may contact either Adult Protective Services or activate Emergency Medical Services (911), as appropriate, to ensure the safety of the subject. The subject will be notified if such a report is filed.

##### IV.b. Potential Benefit to Subjects

The potential benefits to home visit subjects specifically are as follows: (1) the possible diagnosis of unsuspected depression, anxiety, or cognitive disorders, for which the subjects would then be able to receive prompt treatment (through referrals to physicians in the appropriate neurological or psychiatric clinic at NYU or comparable clinic(s) of their choice). The potential benefits to all subjects are as follows: (1) the satisfaction of having contributed to scientific knowledge about progressive supranuclear palsy and related disorders that may help to increase the quality of life of themselves and other subjects with movement disorders. The potential impact of this and future studies is a model of care to improve quality of life and caregiver strain for thousands of individuals with PRD. The potential benefit to society includes: (1) increasing the independence, quality of life, and productivity of patients with PRD, (2) extending medical treatment, psychosocial support, and health education into the home, (3) enhancing patient safety, (4) increasing patient access to care, (5) reducing hospital readmissions and admissions to long-term care facilities, (6) reducing caregiver strain, and (7) decreasing healthcare utilization and

costs. In our opinion, the individual and societal benefits clearly outweigh the minimal risks of participation in this study.

#### V. Subject Identification, Recruitment, and Consent/Accent

##### V.a. Method of Subject Identification and Recruitment

Patients who are under care of the PI or any referring movement disorders provider at the Rush University Parkinson's Disease and Movement Disorders Program who meet the inclusion criteria for this study, will be offered further information about the study by their treating neurologist at the time of or after their routine office visit, directed to an available study team member for additional information, or will be screened and contacted directly by the study team. Subjects who are interested in participating will be given further information about the study. Subjects living within the catchment area but seen at other institutions may receive information about the study through their involvement with local CurePSP support groups. Support groups will provide the IRB-approved recruitment fliers to their participants, with contact information for the study team. Upon contacting the study team, the team member will review the eligibility criteria with the potential participant; if met, the team member will proceed with scheduling the first study visit, at which time the consent process will take place as described below.

##### V.b. Process of Consent

**Home visit subjects:** Subjects will be asked to carefully read the respective IRB-approved Informed Consent Form. The trained research study team member, will obtain consent in a private, distraction-free area in the patient's home. The person obtaining written informed consent from the subject will assess capacity to participate in the research study. It is not practicable to have an individual independent of the study team perform the capacity assessment or obtain informed consent because both are done in the potential subject's home, and both space and funding limit the number of individuals who can practically attend a visit.

Subjects who consent to be contacted about future studies will be notified of potential studies that they are eligible for as studies are available for recruitment. Their consent to participate in the CarePSP study does not apply to other studies. As such, subjects will have to go through the respective consent processes separately. Subjects have the right to refuse participation in any study without consequence to their participation in the registry or their routine patient care. Subjects will be informed about their right to request not to be contacted for specific periods of time or to discontinue active participation in the program, although their data will continue to be stored for future use.

**Usual care subjects:** We have incorporated the components of the informed consent document into the first page of the online survey. Potential subjects must read through the informed consent language on the first page and click a button agreeing to continue. On the next page of the survey, we have incorporated capacity assessment questions to ensure understanding of the consent process. Following correct completion of these questions, the potential subjects are then directed to the actual survey questions.

##### V.c. Subject Capacity

Capacity to consent will be assessed by the designated trained research staff member and/or the PI. Throughout the consent process, the study staff member will assess the participant's comprehension by asking the participant to verbally summarize key elements of the consent form particularly the sections of the consent form that explains that they are being asked whether they agree to be contacted for other studies, as well as aspects of the consent form that explain the inclusion of PHI in the database, how their confidentiality will be protected, and how their data will be stored for future use.

Subject's capacity is not expected to fluctuate significantly, however cognitive fluctuations can be seen in some PRD patients with dementia, such that an individual varies from having capacity to not having capacity, and back again within the span of hours. If in the course of the routine clinical activities of the visit, the clinical or study team members are concerned about capacity, the study team will reassess capacity by asking the original capacity assessment questions. If the subject no longer has capacity, then surrogate consent would be required to proceed with the study visit; if no surrogate, the subject would be withdrawn from the study but would not be dropped from the clinical program providing their care. Subjects who regain capacity at a subsequent clinical visit would need to provide self-consent again. Subjects who refuse capacity assessment cannot be in the study.

During the consent process, subjects will have the opportunity to indicate whether they wish to be contacted for participation in future studies conducted by researchers at Rush and their collaborators or only be part of CarePSP. Subjects who agree to participate in the program will also have an opportunity to authorize having their Personal History Information (PHI) shared with our collaborators. PHI data will **NOT** be shared unless written authorization is obtained from the subject.

Home visit subjects will be given a copy of the signed IRB approved Informed Consent Form for their future reference. Signed consent forms will be stored in a locked cabinet in the PI's office at Rush, separate from the study data.

Subjects who are unable to provide meaningful written, informed consent due to cognitive deficits will be asked whether their caregiver may provide informed consent. The caregiver (i.e. next of kin, health care proxy, court appointed LAR, etc.) will then be asked to give consent for participation in the study as above, with assessment of capacity as above. If the subject does not have a caregiver that is able to provide consent for the subject, the subject will not be eligible to enroll in the study. If subject does have a caregiver, and the caregiver has capacity to consent and provides informed consent, the subject will be asked for assent to participate, as stipulated in the Alzheimer's Association's recommendations for research consent for cognitively impaired adults. If the subject provides assent or does not dissent, then the subject may be enrolled.

#### V.d. Debriefing Procedures

Subjects will not be debriefed about the aims and study hypotheses following administration of all study procedures due to the nature of the study and the data collected.

#### V.e. Documentation of Consent

A Consent Process Documentation Form will be included in the home visit subjects' research chart that will document the informed consent process that took place. For usual care subjects, their online survey data will contain an indicator that they have read and agreed to the consent language.

#### V.f. Costs to the Subject

Subjects will not receive any inducements before, or rewards or compensation (i.e. cash, taxi fares, medical care, gifts, etc.) after the study. There will be no cost to subjects associated with participation in this study.

Statistical Analysis Plan: In-Home Care for Patients with PSP and Related Disorders

NCT03552484

3-18-2019

Outcome ascertainment

Primary outcomes. The EQ5D will be completed at Visits 1-4 for program patients and annually for controls. This scale measures 5 domains of quality of life: *mobility, self care, usual activities, pain/discomfort, anxiety/depression*; each domain is scored from 1 to 5, with higher scores indicating better function. The scale also includes one item measuring overall self-rated health on a visual analogue scale (VAS) from 0 to 100, where 100 is “best health you can imagine”. This generic scale has been studied in PSP and related disorders and is available in an online format, supporting the feasibility of our control group. Change will be assessed in each EQ5D domain and in the VAS between baseline and 1 year. The instrument will also be administered at Visits 2 and 3 to avoid missing data if dyads are lost to follow-up prior to Visit 4. The MCSI will be completed at Visits 1-4 for caregivers, and annually for control caregivers. This scale is scored from 0-72, with 20-29 indicating moderate strain, 30 or higher indicating severe strain. MCSI scores will be evaluated as both continuous and categorical variables.

Demographics and confounders. include *race, ethnicity, education, insurance*, for patients and caregivers respectively; *living situation* (home or nursing facility), *diagnosis, diagnosis duration* (from year of onset or diagnosis, if onset unknown), and *comorbidities*.

Other variables of interest. The following items will be evaluated in program patients only: *hallucinations, motor severity (UPDRS, HY), and satisfaction* with the program (*Client Satisfaction Index-Short Form, CSI-SF*) administered to patients and caregivers.

Power calculation: Based on pilot recruitment, we anticipate enrolling 20 patients in home visits over 12 months, with a 15% drop out rate, yielding 17 patients at 12 months. We anticipate enrolling 100 control patients and 60 control caregivers, with a 20% drop out rate, yielding 80 patient and 48 caregiver controls. To detect a minimum clinically important difference of 6.5-8.0 in the EQ5D VAS, assuming a baseline mean of 37, standard deviation of 18, power of 0.80 and two-sided alpha of 0.05, we would require 42-63 patients.

Data management: The primary data will be entered into a HIPAA-compliant database (**REDCap**), with quarterly audits for fidelity. Data will be exported to Stata 14 for analysis.

Data analysis:

Descriptive statistics. We will describe the demographics, disease characteristics, QoL, and caregiver strain at baseline in patients and caregivers. Categorical variables will be summarized by frequencies and percentages. Continuous variables will be assessed for normality and summarized by mean and standard deviation, or median and interquartile range. Adequacy of matching will be evaluated using chi-square and *t*-tests.

Bivariate analyses. Change in EQ5D subscores and VAS over 1 year will be compared between groups, stratified by diagnosis, by two-sample *t*-test or nonparametric Wilcoxon rank sum test. If a subject dies or is lost to follow-up, the last values of the EQ5D will be carried forward. We will analyze the association with change in EQ5D for each demographic, confounder, and covariate via chi square or multivariate ANOVA, as appropriate. We will compare change in MCSI over 1 year by group, stratified by diagnosis; if lost to follow-up, the last MCSI value will be carried forward.

Multivariable analyses. We will construct a linear regression model with change in EQ5D domains and VAS as sequential dependent variables, and treatment status as the primary independent variable, stratifying by diagnosis. We will build complex models to assess the contributions of each significant covariate. Model building will include manual stepwise, backward elimination checking for multicollinearity and confounding. We will construct similar models wherein MCSI change is the dependent variable.

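### Five EQ5D domains and the VAS are unranked primary results: the plan does not say which one decides the between-group part of hypothesis 1, and it has no multiplicity rule

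*SAP*

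**What the plan says.** Protocol I.a, hypothesis 1, has two parts: home-visit patients improve from enrollment to one year, and they have better quality of life at one year than controls. Both rest on change in EuroQoL-5 scores, with no component named.

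The SAP puts the EQ5D under Primary outcomes and states: "Change will be assessed in each EQ5D domain and in the VAS between baseline and 1 year". With five domains and one VAS, that is six results. Under Bivariate analyses: "Change in EQ5D subscores and VAS over 1 year will be compared between groups, stratified by diagnosis". Under Multivariable analyses the regression takes "change in EQ5D domains and VAS as sequential dependent variables", with treatment status as the main independent variable. In context, sequential means one model after another; no testing order or stopping rule is attached.

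The Power calculation paragraph uses the VAS alone: "To detect a minimum clinically important difference of 6.5-8.0 in the EQ5D VAS", with SD 18, power 0.80 and two-sided alpha 0.05, "we would require 42-63 patients". That is the only place where alpha appears. Neither document ranks the six, defines an index score, says how many must be positive, or adjusts for multiplicity. Protocol II.a calls the study exploratory.

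**The concern.** All six results are listed in advance, so a reader of the final report can see that six were tested. The reader cannot see which one was meant to decide. If one domain is significant and the other five results are not, the plan gives no basis for saying whether hypothesis 1 is supported. An isolated positive could be presented as the primary finding, and nothing in either document would contradict it.

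**Working it through.** **Step 1. The plan's own sample size.** Inputs from the SAP's Power calculation: difference 6.5 to 8.0 VAS points, SD 18, power 0.80, two-sided alpha 0.05.
- One-sample or paired t-test, solved with the noncentral t: 41.7 at 8.0 points and 62.1 at 6.5 points, which round up to 42 and 63. This reproduces the stated range. (The normal approximation, ((1.960 + 0.842) × 18 / difference)², gives 40 and 61.)
- Two-sample, 1:1, normal approximation, 2 × ((1.960 + 0.842) × 18 / difference)²: 80 and 121 per arm. This does not reproduce the range.

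The sizing sentence therefore fits a within-group change. It cannot be read as naming the VAS as the deciding between-group result.

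**Step 2. Chance of a false claim of benefit.** Inputs: six results (SAP, Primary outcomes) and two-sided 0.05, which is 0.025 in the favourable direction. Hypothesis 1 is directional, so only results favouring home visits count. The any-one-counts rule is an assumption.
- One test: 0.025.
- Six independent tests: 1 − 0.975⁶ = 0.141.
- Six equally correlated normal test statistics, chance that at least one exceeds 1.96: 0.122 at correlation 0.3, 0.104 at 0.5 and 0.082 at 0.7. The documents give no correlation, so these values are assumed.

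**Step 3. One named outcome against a six-way Bonferroni correction.** Inputs: 17 home-visit and 80 control completers (SAP). SD 18 is assumed to apply to change; the documents give no SD of change, so a range of 14 to 22 is shown. Power is for an unadjusted two-sample t-test at differences of 6.5 and 8.0 points. Bonferroni alpha is 0.05 / 6 = 0.0083. The 95% CI half-width is t(0.975, 95 df) × SD × √(1/17 + 1/80) = 1.985 × SD × 0.267.

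| SD of change | Power at 0.05 | Power at 0.05/6 | CI half-width, points |
|---|---|---|---|
| 14 | 0.406 and 0.563 | 0.176 and 0.295 | 7.4 |
| 18 | 0.268 and 0.377 | 0.095 and 0.158 | 9.5 |
| 22 | 0.195 and 0.271 | 0.060 and 0.097 | 11.7 |

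Bonferroni costs more power than naming one outcome at every SD. Power is low either way.

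**The case against.** The strongest reply is that formal error control is out of place here. The Protocol calls the study exploratory. The arms are not randomised: one is homebound, local and interviewed in person, while the other answers an online survey. Confounding means that even a single test does not have an assured 5% error rate. All six results are declared, so a reader can discount an isolated positive. This stands as a limit on severity. It does not settle the point, because the SAP names primary outcomes, sizes on a two-sided alpha of 0.05, and nowhere says that p-values are descriptive only.

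A second reply is that the VAS is implicitly primary because it alone was used for sizing. The SAP does not say so, and Step 1 shows that the sizing is not for the between-group contrast.

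A third reply is that naming one outcome does not by itself produce one prespecified test, since the SAP builds its models by stepwise elimination. This is right, and the fix takes it in.

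Three stronger readings are tempting, but the documents do not support them:
- A reader might quote 1 − 0.95⁶ = 26%. That counts results favouring controls, which could not support a hypothesis of benefit.
- A reader might multiply the six by the diagnosis strata. The number of strata is not fixed, and the SAP does not say whether stratifying means separate fits or adjustment.
- A reader might add the MCSI because "MCSI scores will be evaluated as both continuous and categorical variables". The analysis section describes only MCSI change ("We will construct similar models wherein MCSI change is the dependent variable") and specifies no categorical test, so there is no extra test to count.

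**Conclusion.** The point holds and is of modest severity: it should be fixed, but it does not undermine the study. Six unranked primary results bear on one directional hypothesis with no deciding rule. Under an any-one-counts rule, the chance of a false claim of benefit is 8% to 14%, against 2.5% for one test. This rests on that rule, which the documents neither state nor exclude, and on assumed correlations from 0.7 down to zero. It covers multiplicity only.

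The power figures rest on SD 18 applying to change, on an unadjusted comparison and on the SAP's completer numbers. A reader might infer better power by counting everyone enrolled, since "If a subject dies or is lost to follow-up, the last values of the EQ5D will be carried forward". That does not follow. Controls are surveyed at baseline and again at 12 months (Protocol III, Usual care/controls), so a control lost in between carries forward zero change and not a 12-month observation.

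**What to change.** State under Primary outcomes that the between-group difference in 12-month change in EQ5D VAS is the single deciding result for the between-group part of hypothesis 1. The VAS is proposed because it is the only outcome with planning figures. The sponsor may name another single outcome, provided this is done before analysis.

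Take the result from one regression of VAS change on treatment status, with all diagnoses in one model and diagnosis as a covariate. List that model's covariates in advance and do not choose them by stepwise elimination; otherwise one named outcome does not secure the 0.05 error rate. Report the five domains and the per-diagnosis results as secondary estimates with 95% CIs and no claim of significance. Because power is low, lead with the VAS estimate and its 95% CI (half-width about 9.5 points at SD 18).

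Cost: a few sentences and a covariate list, with no extra patients or data. If stratifying by diagnosis meant separate fits, this is one additional model. There are two downsides. A benefit confined to one domain could not by itself decide hypothesis 1. The within-group part of hypothesis 1 becomes supportive unless the sponsor names a deciding result for it.

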#### Characteristics of the Research Population

##### II.a. Number of Subjects

Total Number of Subjects in Home Visit and Usual Care arms: 85

Number of Subjects in Home Visit Arm: 25 subjects with Progressive supranuclear palsy, multiple system atrophy, corticobasal syndrome, or atypical parkinsonism. Participation in the home visit arm neither requires nor prohibits participation in the survey pilot phase.

Number of Subjects in Usual Care Arm: 60 subjects with Progressive supranuclear palsy, multiple system atrophy, corticobasal syndrome, or non-idiopathic PD atypical parkinsonism. Participation in the usual care arm neither requires nor prohibits participation in the survey pilot phase.

This is an exploratory study; no power analysis was conducted. The number of home visit subjects was projected based on recruitment to pilot work at NYU and discussions with Rush colleagues regarding feasibility. The number of control subjects was based on discussions with CurePSP senior staff regarding the size of their support group and social media-connected networks.

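### The SAP's requirement of 42-63 patients fits a one-sample test; the planned two-group comparison has only about 27-38% power at 17 versus 80 patients

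*SAP*

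**What the plan says.** The SAP (Power calculation) expects 20 home-visit patients, "with a 15% drop out rate, yielding 17 patients at 12 months". For the comparison arm it says "We anticipate enrolling 100 control patients and 60 control caregivers", with 20% dropout leaving 80 control patients. The next sentence gives the sample size. It begins "To detect a minimum clinically important difference of 6.5-8.0 in the EQ5D VAS", assumes a baseline mean of 37 and a standard deviation of 18, and ends "power of 0.80 and two-sided alpha of 0.05, we would require 42-63 patients". It does not name the test, say whether the figure is per arm or in total, or relate it to the 17 and 80 patients just mentioned.

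The SAP (Bivariate analyses) then specifies the comparison: "Change in EQ5D subscores and VAS over 1 year will be compared between groups, stratified by diagnosis, by two-sample" t-test or Wilcoxon rank sum test. The multivariable models have treatment status as the main independent variable. The EQ5D is listed among the primary outcomes. Protocol section I.a hypothesises both an improvement from enrolment in the home-visit group and better quality of life than controls at one year.

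Protocol section II.a says "This is an exploratory study; no power analysis was conducted" and "Total Number of Subjects in Home Visit and Usual Care arms: 85", made up of 25 home-visit and 60 usual-care subjects.

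**The concern.** A required sample size has to belong to the test that will be run. A two-group comparison carries the sampling error of both groups, so at equal allocation it needs about four times the total of a one-sample test with the same difference and standard deviation. When one group is as small as 17, adding controls helps little, because the small group dominates the standard error.

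The paragraph puts 17 and 80 expected completers directly before a requirement of 42-63. A reader who adds 17 + 80 = 97, or takes the protocol's 85, will conclude that the between-group test has at least 80% power for the minimum clinically important difference. If it does not, a null result could be misread as evidence that the programme fails to reach that difference.

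**Working it through.** **Inputs (SAP, Power calculation).** Difference δ = 6.5 to 8.0 VAS points; SD 18; power 0.80; two-sided alpha 0.05; 20 × 0.85 = 17 home-visit patients and 100 × 0.80 = 80 controls at 12 months.

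**Step 1: reproduce 42-63.** One-sample or paired t-test, with noncentrality δ√n / SD and n − 1 degrees of freedom. The smallest n with power of at least 0.80 is:

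- δ = 8.0: n = 42 (power 0.803; n = 41 gives 0.793)
- δ = 6.5: n = 63 (power 0.806; n = 62 gives 0.799)

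Both ends match exactly. The normal approximation, (18 × (1.960 + 0.842) / δ)², gives 40 and 61.

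**Step 2: the planned two-group test, same inputs.** Noncentrality δ / (SD × √(1/n₁ + 1/n₂)), with n₁ + n₂ − 2 degrees of freedom.

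| Allocation | δ = 8.0 | δ = 6.5 |
|---|---|---|
| 1:1 | 81 per group, 162 in total | 122 per group, 244 in total |
| 17:80 | 49 + 231 = 280 | 74 + 348 = 422 |

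**Step 3: power at the sizes in the documents.** For 17 versus 80 the standard error is 18 × √(1/17 + 1/80) = 4.81, so the noncentrality is 6.5 / 4.81 = 1.35 or 8.0 / 4.81 = 1.66.

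| Home visit vs control | Source | δ = 6.5 | δ = 8.0 |
|---|---|---|---|
| 17 vs 80 | SAP, at 12 months | 27% | 38% |
| 20 vs 100 | SAP, all enrolled | 31% | 44% |
| 25 vs 60 | Protocol, all enrolled | 32% | 45% |
| 21 vs 48 | Protocol sizes after the SAP's dropout (25 × 0.85 ≈ 21; 60 × 0.80 = 48) | 27-28% | 39% |

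The difference detectable with 80% power at 17 versus 80 is about (1.960 + 0.842) × 4.81 = 13.5 by the normal approximation and 13.6 by exact t. That is 13.6 / 8.0 = 1.7 to 13.6 / 6.5 = 2.1 times the stated minimum clinically important difference.

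**Step 4: which standard deviation?** The SAP gives 18 next to the baseline mean, but the endpoint is change. If 18 is cross-sectional and equal at both times, the SD of change is 18 × √(2(1 − r)), where r is the correlation between baseline and one year. This equals 18 only if r = 0.5. Neither document gives r, so the values below are assumptions.

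| r (assumed) | SD of change | Power, 17 vs 80: δ = 6.5 / 8.0 |
|---|---|---|
| 0.3 | 21.3 | about 20% / 29% |
| 0.5 | 18.0 | 27% / 38% |
| 0.8 | 11.4 | 56% / 74% |

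At 17 versus 80, 80% power would need r of about 0.83 for 8.0 points and 0.89 for 6.5.

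**The case against.** **The SAP never says one-sample, and it has a within-group hypothesis.** The test is indeed inferred, from an exact match at both ends. A one-sample size would be the right type for the hypothesised improvement from enrolment. Even so, 17 patients is far below 42 and gives 29% / 41% power for 6.5 / 8.0 points; 25 patients give 41% / 57%. The between-group comparison would then have no sample-size figure at all.

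**The range might be per group.** That would need an SD of change of about 12.9 (r about 0.74), which the SAP does not state, and 17 would still be short of 42.

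**The SAP does not claim adequate power, and the protocol calls the study exploratory.** Both are true. The requirement is worded conditionally and the 17 is in plain view. Exploratory status excuses low power, but not a requirement computed for a different test. The protocol's statement that no power analysis was done contradicts the SAP's power section and does not correct it.

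**Last values are carried forward, and r may be high.** This part stands as a limit on the figures. With all enrolled patients analysed and r = 0.8, power for 8.0 points is 81% at 20 versus 100 and 83% at 25 versus 60; at r = 0.85, 17 versus 80 reaches 85%. At r = 0.8, power for 6.5 points stays below 80% in all these sets. The restated power should therefore be a range, not a single figure.

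**Conclusion.** The concern holds. On the SAP's own inputs, 42-63 is a one-sample or paired sample size, while the planned comparison is between two groups. That comparison needs 162-244 patients at equal allocation, or about 280-422 at 17:80, and has about 27-38% power with the 17 and 80 patients expected at 12 months.

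These power figures assume that 18 is the SD of change, equal variances and an unstratified t-test. Over assumed correlations of 0.3 to 0.8, power at 17 versus 80 stays below 80%. Higher correlations, or the upper end of that range with all enrolled patients analysed, could reach 80% for 8.0 points, but nothing in the documents supports a particular value. Stratification by diagnosis is not in these figures; separate analyses within each diagnosis would have less power.

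The conflicts over arm sizes and over whether a power analysis was done are a separate matter of consistency, but they affect the same paragraph. The statement must be corrected because it is the SAP's only sample-size justification.

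**What to change.** Replace the last sentence of the SAP's power paragraph with one that describes the planned test, for example:

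> With 17 home-visit and 80 control patients at 12 months and two-sided alpha 0.05, a two-sample t-test of change in VAS has about 27% power for 6.5 points and 38% for 8.0 if the SD of change is 18; 80% power is reached at about 13.6 points. If the SD of change lies between 21.3 and 11.4, power runs from about 20% / 29% to 56% / 74%. The study is exploratory, and results will be reported as estimates with 95% confidence intervals.

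In addition:

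- State whether 18 is the SD at baseline or the SD of change, and give its basis.
- If the 42-63 is kept for the within-group hypothesis, label it as such and say that the expected 17 falls short of it.
- Settle the arm sizes (25 + 60 or 20 + 100) and recompute the figures for those sizes and for the intended analysis set.
- Make the protocol's statement that no power analysis was done agree with the SAP.

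The cost is wording in both documents. No extra patients are needed and no analysis changes, but the plan will then show openly that the between-group comparison has low power for the stated difference.
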